3.1.8 Evaluation of Biomarkers

In Part D, E and D Extension, blood samples for the analysis of galactose, galactitol, and galactose-1-phosphate and urine samples for the analysis of galactitol will be collected. With the exception of the blood samples for biomarkers taken at Screening and Day -1, the time points and allowable windows for the blood samples for biomarkers will match those for the blood samples for PK.

3.2 Evaluation of Treatment Safety

3 2 1 Adverse Events

Adverse events will be monitored from the time the subject signs the informed consent throughout the study. AEs will be collected for each subject from the time of informed consent through the EOS (or EOE) Visit. The following details will be collected: description of the AE, start date and time, stop date and time, action taken with study treatment (dose not changed, dose reduced, drug interrupted, drug withdrawn, dose increased, not applicable), outcome (recovered/resolved, not recovered/not resolved, recovered/resolved with sequelae, recovering/resolving, fatal, unknown), severity (mild, moderate, severe), seriousness (yes, no), relationship to study drug (not related, unlikely related, possibly related, probably related). An AE is considered "unexpected" if the AE is not listed in the Investigator Brochure or is not listed with the observed specificity or severity.

3.2.2 Clinical Laboratory Assessments

A Clinical Laboratory Improvement Amendments certified laboratory will perform the following clinical laboratory tests:

- Hematology: hemoglobin, hematocrit, total and differential leukocyte count, RBC, and platelet count
- Serum chemistry: albumin, blood urea nitrogen (BUN), creatinine, total bilirubin, alkaline phosphatase (ALP), aspartate transaminase (AST), alanine transaminase (ALT), sodium (Na+), potassium (K+), chloride (Cl-), lactate dehydrogenase (LDH), calcium (Ca), uric acid, glucose, direct bilirubin (DB), and gamma-glutamyl transferase (GGT)
- Coagulation: prothrombin time (PT) and international normalized ratio (INR)
- Serology: blood tests for hepatitis B surface antigen, hepatitis C antibody, and HIV.
- Urinalysis by an automated or manual urine "dipstick" method: pH, specific gravity, protein, glucose, ketones, bilirubin, blood, nitrite, leukocyte esterase, and urobilinogen. If protein, occult blood, nitrite, or leukocyte esterase values are out of range, a microscopic examination will be performed.
- Urine drug screen: drugs of abuse (amphetamines, benzodiazepines, barbiturates, cannabinoids, cocaine, opiates)
- Urine cotinine screen (subjects in Parts A, B, and C only)
- Pregnancy test (all female subjects of childbearing potential)
- FSH (for female subjects claiming postmenopausal status)

For Parts D, E and D Extension only, the following tests will be done in addition to the ones listed above:

- GALT (Part D and Part D Extension but only done once for subjects participating in both Parts) or GALK (Part E) activity in red blood cells
- GALT (Part D and Part D Extension but only done once for subjects participating in both Parts) or GALK (Part E) gene analysis
- Aldose Reductase activity (only done once for subjects participating in both Parts D and D Extension)

Fasted samples for hematology, coagulation, chemistry, and urinalysis assessments will be collected at the following time points:

- Part A: Screening, Day -1, Day 3, EOS
- Part B: Screening, Day -1, Day 6, EOS
- Part C: Screening, Day -1, Day 6, EOS
- Part D: Screening, Days -1, 6, 12, 20, 32, EOS

- Part E: Screening, Days -1, 6, 12, 20, 32, EOS
- Part D Extension: Screening, Days -1, 30, 60, 90, EOE

3.2.3 Vital Signs

Vital signs (blood pressure, pulse rate, respiration rate, and temperature) will be measured as follows:

- Part A: Screening, Day -1 check-in, predose (within 60 min before the dose) on Day 1, at 4 hours (±10 minutes) after the dose on Day 1, once daily on Days 2 and 3, and EOS
- Part B: Screening, check-in on Days -1 and 6, predose (within 60 min before the dose) on Days 1 and 7, at 4 hours (±10 minutes) after the dose on Days 1 and 7, once daily on Days 2, 8, and 9, and EOS
- Part C: Screening, check-in on Days -1 and 6, predose (within 60 min before the dose) on Days 1 and 7, at 4 hours (±10 minutes) after the dose on Days 1 and 7, once daily on Days 2, 8, and 9, and EOS
- Part D: Screening, every check-in, every check-out, predose (within 60 min before the dose) and 4 hours (±10 minutes) after the dose on Days 1, 6, 12, 20, and 32, once daily on all other in-clinic days, and EOS
- Part E: Screening, every check-in, every check-out, predose (within 60 min before the dose) and 4 hours (±10 minutes) after the dose on Days 1, 6, 12, 20, and 32, once daily on all other in-clinic days, and EOS
- Part D Extension: Screening (if applicable), every check-in, every check-out, predose (within 60 min before the dose) and 4 hours (±10 minutes) after the dose on Days 1, 30, 60, and 90, once daily on all other visits, and at the EOE visit.

Additional vital signs measurements may be taken as deemed medically necessary by the Investigator/designee. For purposes of qualifying any given subject for study participation, out of range vital signs may be repeated once.

All vital signs measurements will be taken with the subject in a seated position and after the subject has been resting in that seated position for at least 5 minutes. Any time during the study after the first dose of study drug, abnormal vital sign measurements considered to be clinically significant by the Investigator/designee will be reported as AEs.

3.2.4 Electrocardiograms

The ECGs will be performed as follows:

- Part A: Screening, Day -1 check-in, predose (within 60 min before the dose) on Day 1, at 2 hours (±10 minutes) after the dose on Day 1, on Day 3, and EOS
- Part B: Screening, Day -1 check-in, predose (within 60 min before the dose) on Days 1 and 7, at 2 hours (±10 minutes) after the dose on Days 1 and 7, and EOS
- Part C: Screening, Day -1 check-in, predose (within 60 min before the dose) on Days 1 and 7, at 2 hours (±10 minutes) after the dose on Days 1 and 7, and EOS
- Part D: Screening, Day -1 check-in, predose (within 60 min before the dose) and 2 hours (±10 minutes) after the dose on Days 1, 6, 12, 20, and 32, and EOS
- Part E: Screening, Day -1 check-in, predose (within 60 min before the dose) and 2 hours (±10 minutes) after the dose on Days 1, 6, 12, 20, and 32, and EOS
- Part D Extension: Screening, Day -1 check-in, predose (within 60 min before the dose) and 2 hours (±10 minutes) after the dose on Days 1, 30, 60, and 90, and EOE

All ECGs will be done with the subject in a supine position and after the subject has been resting in that supine position for at least 5 minutes.

3.2.5 Physical Examinations

Physical examinations will be performed as follows:

- Part A: Screening; Days -1 and 3; and EOS
- Part B: Screening; Days -1, 6, and 9; and EOS
- Part C: Screening; Days -1, 6, and 9; and EOS
- Part D: Screening; Days -1, 6, 12, 20, 32, and 34; and EOS
- Part E: Screening; Days -1, 6, 12, 20, 32, and 34; and EOS
- Part D Extension: Screening; Days -1, 30, 60 and 90; and EOE

Height will be measured at screening. Weight will be measured as part of all physical examinations. Any time during the study after the first dose of study drug, abnormal findings considered to be clinically significant by the Investigator/designee will be reported as AEs.

3.2.6 Other Safety Assessments

In Parts D and E, brain MRI/MRS will be performed during the Screening Period and toward the end of the MAD treatment (i.e., either on Day 30, Day 31, or Day 32). MRI/MRS will only be performed in a subset of subjects who specifically consent to the brain imaging.

In Part D Extension, brain MRI/MRS will be performed during the Screening Period (unless the subject previously participated in Part D and had a brain MRI/MRS performed during the Screening Period for Part D) and toward the end of the treatment period (i.e., either on Day 88, Day 89, or Day 90). MRI/MRS will only be performed in subjects who specifically consent to the brain imaging.

3.2.7 Protocol Deviation Reporting

Procedural deviations found by the clinical research associate (CRA) during monitoring visits and data deviations captured on the electronic case report form (eCRF) and found through programming and examining the database will be listed by subject.

4 CHANGES IN THE CONDUCT OF THE STUDY OR PLANNED ANALYSIS

There are a few changes in the study conduct or analysis plans relative to the study protocol:

- The objective "To evaluate the effect of single and multiple doses of orally administered AT-007 on the levels of galactose and its other metabolites in adult subjects with CG or GALK-deficient Galactosemia" is a secondary objective according to the study protocol, but it should be an exploratory objective only.
- The secondary endpoint "Galactose, galactitol, and other galactose metabolites in the blood of subjects with CG and subjects with GALK-deficient Galactosemia" was replaced by "Galactitol in the blood of subjects with CG and subjects with GALKdeficient Galactosemia" and the exploratory endpoint "Galactose and galactose metabolites in the blood of subjects with CG and subjects with GALK-deficient Galactosemia" was added.
- Additional subgroup analysis performed for Part D blood and urine Galactitol will be performed if data permit.
- Urine galactitol concentrations for each collection interval will also be presented normalized to urine creatinine.
- The DBL will be carried out after the completion of Part D and CSR will be written for Part A to D. This will lead to unblinding of Part A and Part B subjects to the study team. Part D- Extension will be carried out as CSR addendum.

5 QUALITY CONTROL AND QUALITY ASSURANCE METHODS FOR DATA ANALYSIS

Case report forms will be monitored and collected by ICON. All monitored eCRFs will be sent to the Data Management group at ICON and processed according to the ICON Study Specific Procedure SSP DM-48480001.01 Data Management Plan (DMP). The DMP describes eCRF data processing, edit checks, data query management, medical dictionary coding, SAE reconciliation, data transfers, and data quality review through database lock or any necessary reopening of the database. After database lock, the data will be retrieved from the database using SAS® version 9.4 or higher.

6 PHARMACOKINETIC ASSESSMENTS

6.1 Pharmacokinetic Assessments

6.1.1 Pharmacokinetic Analysis

Pharmacokinetic parameters will be calculated from the plasma concentration-time data using noncompartmental techniques (Phoenix WinNonlin[®], Build 8.0.0.3176 or higher, Certara L.P. (Pharsight), St. Louis, MO) and actual sampling times. PK parameters will also be determined using the urine concentration data collected over 48 hours after dosing (Cohort A4 and A5).

For subjects in Part C, a Day 7 lumbar puncture will be done to collect CSF for AT-007 measurement using a qualified assay.

The PK parameters in Table 6-1 will be determined for the SAD parts of the study (i.e. Part A the single dose period of Part D and E).

Table 6-1: Pharmacokinetic Parameters of AT-007 After a Single Dose in Healthy Subjects (Part A) and Subjects with Classic Galactosemia (Single Ascending Dose Period of Part D and E)

| Parameter | Definition |
|---------------------------|--|
| C _{max} | Maximum concentration, determined directly from individual concentration time data |
| T_{max} | Time of the maximum concentration |
| $\lambda_{\rm z}$ | The observed terminal rate constant; estimated by linear regression through at least 3 data points in the terminal phase of the log concentration-time profile |
| T _{1/2} | The observed terminal half-life, calculated as: $T_{1/2} = \frac{\ln(2)}{\lambda_z}$ |
| AUC _{last} | Area under the concentration-time curve from time-zero to the time of the last quantifiable concentration; calculated using the linear trapezoidal rule |
| AUC _{inf} | Area under the concentration-time curve from time-zero extrapolated to infinity; calculated as: $AUC_{\rm inf} = AUC_{last} + \frac{C_{last}}{\lambda_z}$ |
| AUC _{Extrap} (%) | The percentage of AUC _{inf} based on extrapolation |
| C _{last} | The last quantifiable concentration determined directly from individual concentration-time data |
| T _{last} | Time of the last quantifiable concentration |
| CL/F | Clearance after extravascular administration, calculated as: $CL/F = Dose/AUC_{inf} \label{eq:clearance}$ |
| Vz/F | Volume of distribution in the terminal phase, calculated as: $Vz/F = (CL/F)/\lambda_z \label{eq:Vz}$ |

The PK parameters in Table 6-2will be determined for the MAD parts of the study (ie, Parts B, C, and multiple dosing period in Parts D and E, and Part D Extension).

Table 6-2: Pharmacokinetic Parameters of AT-007 During Multiple Dosing in Healthy Subjects (Parts B and C) and Subjects with Galactosemia (Multiple Ascending Dose Period of Parts D and E and Part D Extension)

| PK Parameter | Definition | |
|---------------------------|--|--|
| C_{max} | Maximum concentration, determined directly from individual concentration time data (Day 1 and Day of Last Dose) | |
| T_{max} | Time of the maximum concentration (Day 1 and Day of Last Dose) | |
| λ_z | The observed terminal rate constant; estimated by linear regression through at least 3 data points in the terminal phase of the log concentration-time profile (Day of Last Dose only) | |
| T _{1/2} | The observed terminal half-life, calculated as: $T_{1/2} = \frac{\ln(2)}{\lambda_z}$ (Day of Last Dose only) | |
| AUC _{tau} | Area under the concentration-time curve during the 24-hour dosing interval; calculated using the linear trapezoidal rule (Day 1 and Day of Last Dose) Note: If quantifiable data are not observed through 24 h postdose, AUC _{tau} will be estimated using extrapolation (from the time of the last reported concentration to 24 h) and AUC _{last} will also be reported. | |
| AUC _{last} | Area under the concentration-time curve from time-zero to the time of the last quantifiable concentration; calculated using the linear trapezoidal rule (Day of Last Dose; Day 1 if quantifiable data are not observed through 24 h postdose) | |
| AUC_{inf} | Area under the concentration-time curve from time-zero extrapolated to infinity; calculated as: $AUC_{\inf} = AUC_{last} + \frac{C_{last}}{\lambda_z} \text{ (Day of Last Dose only)}$ | |
| AUC _{Extrap} (%) | The percentage of AUC _{inf} based on extrapolation (Day of Last Dose only) | |
| C _{last} | The last quantifiable concentration determined directly from individual concentration-time data (Day 1 and Day of Last Dose) | |
| T _{last} | Time of the last quantifiable concentration (Day 1 and Day of Last Dose) | |
| CL/F | Clearance after extravascular administration, calculated as: $CL/F = Dose/AUC_{tau(DayX)}$, where Day $X = Day$ of Last Dose and Dose is the actual dose administered (mg/kg x kg). (Day of Last Dose only) Note: $CL/F/kg$ may also be reported | |
| Vz/F | Volume of distribution in the terminal phase, calculated as: $Vz/F = (CL/F)/\lambda_z$ (Day of Last Dose only) Note: $Vz/F/kg$ may also be reported | |
| Rac | The accumulation ratio during multiple dose administration, based on C_{max} and AUC_{tau} ; calculated as: Rac $(AUC_{tau}) = AUC_{tau}$ $(Day X) / AUC_{tau}$ $(Day 1)$ Rac $(C_{max}) = C_{max}$ $(Day X) / AUC_{tau}$ $(Day 1)$ Note: Rac will be tabulated with the pharmacokinetic parameters on Day X. Note: Day $X = Day$ of Last Dose | |

Note: Day of Last Dose is Day 7 in Parts B and C, Day 32 in in the MAD portion of Part D and E, and Day 90 in Part D Extension

Urine concentration data from Part A4, A5 and Part D3 will be used to determine the following parameters:

Ae Amount excreted into urine, calculated over 72 hours

Fe% Fraction of drug excreted in urine over 72 hours, calculated as Ae/dose X

100%

Only data points that describe the terminal elimination log-linear decline will be used in the regression equation for calculation of terminal elimination phase rate constant; C_{max} and any data point in the distribution phase are not included in the calculation. A minimum of 3 points will be used for determination of the terminal elimination phase rate constant. A general rule of adjusted $R^2 > 0.80$ will be considered as acceptable for calculation of the terminal elimination phase rate constant. If the adjusted R^2 falls below 0.80, then the terminal elimination phase rate constant will be reported as not determined (ND) and that subject's λ_z , $t_{1/2}$, AUC_{inf} , CL/F, and Vz/F will be reported as ND in the appropriate listings. If the extrapolated AUC_{inf} is more than 20%, then AUC_{inf} , CL/F and Vz/F will be listed but excluded from descriptive summaries and statistical analysis.

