

**APPENDIX A. SCHEDULE OF ASSESSMENTS FOR PART A (SAD IN
HEALTHY SUBJECTS)**

Schedule of Assessments for SAD in Healthy Subjects (Part A)

PROCEDURE	Screening (Days -28 to -1)	Day -1 ^a (Check-in)	Day 1	Day 2	Day 3 ^a (Check-out)	Day 4 ^a (Check-out)	EOS Visit ^b (Day 28±2)
Check-in		X ^a					
Discharge					X ^a	X ^a	
Informed consent	X						
I/E criteria	X	X					
Medical history/updates	X	X					X
Demographic data	X						
Physical examination ^c	X	X			X		X
Vital signs ^d	X	X	X	X	X		X
Electrocardiogram ^e	X	X	X		X		X
Clinical laboratory testing (biochemistry, hematology, coagulation, urinalysis, UACR, UPCR) ^f	X	X			X		X
HIV and hepatitis B & C testing	X						
Urine drug/cotinine screen	X	X					
Pregnancy test (female subjects) ^g	X	X			X		X
Drug administration			X				
Blood sample collection for PK analysis ^h			X	X	X		
Urine collection for PK analysis ⁱ (Cohorts A4 and A5 only) ^j			X	X	X	X	
Adverse Events							Throughout Study
Prior/Concomitant medications	X						Throughout Study

EOS = end-of-study; FSH = follicle-stimulating hormone; HIV = human immunodeficiency virus; I/E = inclusion/exclusion; PK = pharmacokinetic;

SAD = single ascending dose; UACR – urinary albumin to creatinine ratio; UPCR = urinary protein to creatinine ratio

a: Check-in will occur around 11 am on Day -1. For Cohorts A1, A2, and A3, discharge from the clinic will occur on Day 3 after all Day 3 procedures are done and blood samples for PK are collected through 48 hours after the dose. For Cohorts A4 and A5, discharge from the clinic will occur on Day 4 after urine for PK is collected through 72 hours after the dose.

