b: The EOS visit will be scheduled for 28 (±2) days after the dose of study drug.

c: All physical examinations will include weight; however, height will be measured only at screening.

d: Vital signs will be measured at Screening, Day -1 check-in, predose (within 60 min before the dose) on Day 1, at 4 hours (±10 minutes) after the dose on Day 1, once daily on Days 2 and 3, and at the EOS visit.

e: Electrocardiograms will be performed at Screening, Day -1 check-in, predose (within 60 min before the dose) on Day 1, at 2 hours (±10 minutes) after the dose on Day 1, on Day 3, and at the EOS visit.

f: Samples for clinical safety laboratory tests will be collected under fasting conditions.

- g: Serum pregnancy tests at Screening, Day -1, and EOS visits; urine pregnancy tests at other time points. Also, female subjects claiming postmenopausal status will have that status verified with an FSH test at Screening. Once a female subject is verified as postmenopausal or otherwise not of childbearing potential, the subject is exempt for further pregnancy tests.
- h: Blood samples for PK will be collected predose (within 60 min before the dose) and at 0.5, 1, 1.5, 2, 4, 6, 8, 12, 24, 36, and 48 hours (\pm 5 minutes for all time points) after the dose.
- i: Urine for PK will be collected predose (spot collection within 60 min before the dose) and in 4-hour intervals (0 to 4, >4 to 8, >8 to 12, >12 to 16, >16 to 20, and >20 to 24) through the first 24 hours after the dose followed by 12-hour intervals (>24 to 36, >36 to 48, >48 to 60, and >60 to 72) from 24 hours postdose to 72 hours postdose. Allowable windows for urine collection container changes will be \pm 30 minutes through the first 24 hours and \pm 1 hour thereafter.
- j: Cohort A4 = highest originally planned dose level cohort in Part A. Cohort A5 = highest planned dose level cohort in Part A after the protocol amendment resulting in protocol version 4.0.

**APPENDIX B. SCHEDULE OF ASSESSMENTS FOR PART B (MAD IN
HEALTHY SUBJECTS)**

Schedule of Assessments for MAD in Healthy Subjects (Part B)

PROCEDURE	Screening (Days -28 to -1)	Day -1 ^a (Check-in)	Day 1	Day 2	Days 3, 4, & 5	Day 6	Day 7	Day 8	Day 9 ^a (Check-out)	EOS Visit ^b (Day 35±2)
Check-in		X ^a								
Discharge									X ^a	
Informed consent	X									
I/E criteria	X	X								
Medical history/updates	X	X								X
Demographic data	X									
Physical examination ^c	X	X				X			X	X
Vital signs ^d	X	X	X	X		X	X	X	X	X
Electrocardiogram ^e	X	X	X				X			X

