3.1.7 Pharmacokinetic Sampling Schedule

In Part A, blood samples for plasma AT-007 PK will be collected predose (within 60 min before the dose) and at 0.5, 1, 1.5, 2, 4, 6, 8, 12, 24, 36, and 48 hours (±5 minutes for all time points) after the dose.

For Part A, Cohort A4 and A5, urine samples for AT-007 PK will be collected predose (spot collection within 60 min before the dose) and in 4-hour intervals (0 to 4, > 4 to 8, > 8 to 12, > 12 to 16, > 16 to 20, and > 20 to 24) through the first 24 hours after the dose followed by 12-hour intervals (> 24 to 36, > 36 to 48, > 48 to 60, and > 60 to 72) from 24 hours postdose to 72 hours postdose. Allowable windows for urine collection container changes will be \pm 30 minutes through the first 24 hours and \pm 1 hour thereafter.

In Part B, on Day 1, blood samples for plasma AT-007 PK will be collected predose (within 60 minutes before the dose) and at 0.5, 1, 1.5, 2, 4, 6, 8, and 12 hours (± 5 minutes for all time points) after the dose. On Day 2, blood samples for plasma AT-007 PK will be collected predose (ie, at 24 hours ± 5 minutes after the Day 1 dose and before the Day 2 dose). On Day 7, blood samples for plasma AT-007 PK will be collected predose (within 60 minutes before the dose) and at 0.5, 1, 1.5, 2, 4, 6, 8, and 12 hours (± 5 minutes for all time points) after the dose. Also, blood samples for plasma AT-007 PK will be collected at 24, 36, and 48 hours (± 5 minutes for all time points) after the Day 7 dose; these collections will be taken on Day 8 and Day 9.

In Part C, on Day 1, blood samples for plasma AT-007 PK will be collected predose (within 60 minutes before the dose) and at 0.5, 1, 1.5, 2, 4, 6, 8, and 12 hours (± 5 minutes for all time points) after the dose. On Day 2, blood samples for plasma AT-007 PK will be collected predose (ie, at 24 hours ± 5 minutes after the Day 1 dose and before the Day 2 dose). On Day 7, blood samples for PK will be collected predose (within 60 minutes before the dose) and at 0.5, 1, 1.5,

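### A sentence in SAP 6.1.1 bases urine PK for Cohorts A4 and A5 on 48 hours of urine, which contradicts the 72-hour definitions of Ae and Fe% in the same section and every urine collection schedule

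*SAP*

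**What the plan says.** SAP Section 6.1.1 gives two windows for the same urine data.

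- The opening paragraph, after describing the plasma analysis, says that "PK parameters will also be determined using the urine concentration data collected over 48 hours after dosing (Cohort A4 and A5". Cohort D3 is not mentioned there.
- After Table 6-2, the section says "Urine concentration data from Part A4, A5 and Part D3 will be used to determine the following parameters". The two parameters follow: "Ae Amount excreted into urine, calculated over 72 hours" and "Fraction of drug excreted in urine over 72 hours, calculated as Ae/dose X" 100%.

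The collection schedules give one window.

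- SAP Section 3.1.7 ends the A4 and A5 intervals with "> 48 to 60, and > 60 to 72) from 24 hours postdose to 72 hours postdose", and schedules D3 urine to 72 hours after the Day 1 dose.
- Protocol Appendix A, footnote i, runs the 12-hour intervals "from 24 hours postdose to 72 hours postdose". Footnote a ties discharge of A4 and A5 to this: "discharge from the clinic will occur on Day 4 after urine for PK is collected through 72 hours after the dose".
- Protocol Appendix D, footnote m, has the same 72-hour schedule for D3.
- Protocol Sections 6.4.3 and 6.7.2.3 each include a Day 4 step to complete the urine collection.

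SAP Section 4, which lists departures from the protocol, does not mention the urine window.

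**The concern.** Both statements in SAP 6.1.1 are instructions for the analysis, and for A4 and A5 they cannot both be followed. The protocol does not settle the matter: its PK parameter tables (Tables 8 and 9) contain no urine parameter. The SAP abbreviation list has generic entries for amount and fraction excreted between two times but fixes no times. The window is set only in SAP 6.1.1, and the SAP states no rule for which sentence prevails.

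If an analyst took the opening sentence as the rule, Ae and Fe% for the two healthy-subject cohorts would stop at 48 hours. D3 has only the 72-hour rule and would run to 72. The same parameter name would then cover different windows in the Part A and Part D tables, with the healthy-subject values lower for that reason alone.

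**Working it through.** **Step 1. Reproduce the 72-hour window.** SAP 3.1.7 and Protocol Appendices A and D give six 4-hour intervals and then four 12-hour intervals:

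6 × 4 h + 4 × 12 h = 24 h + 48 h = 72 h, in 10 intervals.

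This matches the window in the definitions of Ae and Fe%.

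**Step 2. Apply the 48-hour sentence.** The intervals end at 4, 8, 12, 16, 20, 24, 36, 48, 60 and 72 h. Eight end by 48 h. The two left out are >48–60 h and >60–72 h, the last 24 h of collected urine.

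**Step 3. Size of the effect on Ae.** The documents give no half-life for AT-007, so a range is assumed. With first-order, mono-exponential excretion and k = ln 2 / t½:

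relative shortfall = 1 − (1 − e^(−48k)) / (1 − e^(−72k))

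For t½ = 12 h, e^(−48k) = 2^(−4) = 0.0625 and e^(−72k) = 2^(−6) = 0.015625, so the shortfall is 1 − 0.9375/0.9844 = 4.76%.

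| Assumed t½ (h) | Excreted by 48 h | Excreted by 72 h | Relative shortfall at 48 h |
|---|---|---|---|
| 4 | 0.9998 | 1.0000 | 0.02% |
| 6 | 0.9961 | 0.9998 | 0.37% |
| 8 | 0.9844 | 0.9980 | 1.37% |
| 12 | 0.9375 | 0.9844 | 4.76% |
| 18 | 0.8425 | 0.9375 | 10.13% |
| 24 | 0.7500 | 0.8750 | 14.29% |
| 36 | 0.6031 | 0.7500 | 19.58% |
| 48 | 0.5000 | 0.6464 | 22.65% |

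The middle columns are fractions of all the drug that would eventually be excreted in urine.

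**Step 4. Fe%.** Since Fe% is Ae divided by dose, the dose cancels in the ratio and the relative shortfall is the same as for Ae.

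**Step 5. After correction.** With one 72-hour window, all 10 intervals count for A4, A5 and D3. The shortfall is zero and the windows match.

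**The case against.** The strongest reply is that the parameter definitions already settle the question. The 48-hour sentence is introductory, names no parameter, and has no 48-hour urine parameter behind it. The definitions name the three cohorts together and give 72 hours, and every schedule agrees. An analyst working from the definitions would get the right answer. This largely stands: 72 hours is the better-supported reading, and the 48-hour figure looks like a slip. Part A plasma sampling does end at 48 hours, which may be where it came from, but the documents do not say. What remains is that the sentence is an explicit instruction for two named cohorts, and it is wrong.

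A reader might infer two further things that the documents do not support.

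- *That the late urine would be thrown away.* SAP Section 7.10 has urine amounts listed by subject and summarised by nominal collection interval, in Tables 14.2.3a and 14.2.3d and Listings 16.2.5.5a and 16.2.5.5d. None of these is limited to 48 hours. The later intervals would be missing from the derived Ae and Fe% only, and the 72-hour amount could be recovered.
- *That a planned comparison of healthy subjects with subjects with Classic Galactosemia would be biased.* The urine parameters for Part A and Part D are separate descriptive outputs (Tables 14.2.4a and 14.2.4d), with no contrast between them. The ongoing comparison of exposure in Protocol Section 5.2 and SAP Section 3.1.3 concerns blood levels of AT-007. A reader could set the two tables side by side, but only informally.

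**Conclusion.** The 48-hour sentence in SAP 6.1.1 is wrong as written: it contradicts the definitions of Ae and Fe% in the same section and all the collection schedules. The point is minor.

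If the sentence were followed, Ae and Fe% for A4 and A5 would omit two of ten intervals and be lower than their 72-hour values by about 0.4%, 5% or 14% for half-lives of 6, 12 or 24 hours. Across the wider assumed range of 4 to 48 hours, the shortfall runs from about 0% to 23%. These figures rest on mono-exponential excretion and on half-lives that the documents do not supply, so they do not show that the effect is material.

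The parameters are descriptive. They are outside the dose-proportionality model in SAP 7.10, which uses AUC and Cmax, and no sample size or type I error depends on them.

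**What to change.** In the opening paragraph of SAP 6.1.1, change 48 hours to 72 hours and name Cohorts A4, A5 and D3, so that the sentence agrees with the parameter definitions later in the section. If a 48-hour value is also wanted, define it as an additional parameter for all three cohorts.

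The cost is an edit to one sentence. Collection, sampling times and planned tables stay as they are, and no new data are needed.
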